ICU duration event/censor variable	
If survived to ICU discharge =Yes and transferred= No on form G, then = 1 If survived to ICU discharge =Yes and transferred= Yes on form G and survived to ICU discharge =Yes on form G2, then = 1 If survived to ICU discharge=No on form G, then = 0 If survived to ICU discharge =Yes and transferred= Yes on form G and survived to ICU discharge =No on form G2, then = 0 Else missing

POPULATION 4:	
Duration of hospital stay	
If survival status = survived to 30 days/hospital discharge and consent=active or consent=passive, then = (Hospital discharge date (Form H/I3) - ED admission date (Form G)) *24*60 + (Hospital discharge time (Form H/I3) - ED admission time (Form G))

New variable	Rules
	
If survival status= died prior to ICU admission or survival status= died prior to ICU discharge or (survival status=died prior to hospital discharge & ((consent status=active or passive) or patient was not approached)), then = (Date of death - ED admission date (Form G)) *24*60 + (Time of death - ED admission time (Form G)) Else missing

Hospital duration event/censor variable	
If survival status =survived to 30 days/ hospital discharge and consent=active or consent=passive, then = 1 If survival status= died prior to ICU admission or survival status= died prior to ICU discharge or (survival status=died prior to hospital discharge & ((consent status=active or passive) or patient was not approached)), then = 0 Else missing

Timing of (patient) withdrawal	
if date of withdrawal from study < date of discharge, then = pre-discharge if date of withdrawal from study > date of discharge, then = post-discharge Else missing

Decision taken by	
if healthcare professional's decision=Yes and (patient choice = No or missing), then = health care professional if healthcare professional's decision=No or missing and patient choice = Yes, then = patient Else missing

1865

1866

1867 **6. STATISTICAL ANALYSES**

1868 **6.1 Baseline data**

1869 Baseline characteristics (i.e. patient demography and initial cardiac arrest details) will be described grouped
1870 by the allocation of the first A2 paramedic on scene for all trial patients (see **Table T4**). Intervention details
1871 will also be described for all trial patients (see **Table T5**).

1872 Continuous variables will be summarised using the mean and standard deviation (SD) (or median and inter
1873 quartile range (IQR) if the distribution is skewed), and categorical data will be summarised as a number and
1874 percentage. The summary statistic headings given in **Tables T4** and **T5** are those we expect to use based on a-
1875 priori knowledge of the clinical measurements gained from previous studies. However, if distributional
1876 assumptions are not satisfied, changes will be made.

1877 Statistical tests to compare data not listed as outcomes will not be performed. Secondary outcomes 4
1878 (sequence of airway interventions delivered) and 7 (airway management in place when ROSC was achieved
1879 or resuscitation discontinued) will be described but not formally compared.

1880 **6.2 Primary and secondary outcome data**

1881 **6.2.1 Adjustment in models**

1882 The intention is to adjust the models for the three stratification (design) factors: ambulance trust (four levels),
1883 clinical experience (two levels) and the location of the paramedic’s base ambulance station (two levels) as
1884 fixed effects, and paramedic as a random effect (or a shared frailty term in the time to event model). For the
1885 mRS model where the majority of patients will have a poor outcome/death, the data may be insufficient to
1886 allow estimation of regression coefficients for all these variables. If this is the case, inestimable stratification
1887 variables will be dropped from the model and will be noted in a footnote. For the time to death model, if a cox
1888 model is used the analysis will be stratified by trust (to allow for varying baseline hazards) and adjusted for
1889 the other design factors. If either of the design factors do not meet the proportional hazards assumptions,
1890 stratification by these factors will also be implemented.

1891 **6.2.2 Data presentation and analysis models**

1892 For intention to treat analyses, data will be presented and analysed by the allocated group of the first A2
1893 paramedic on scene, regardless of what airway management the patient received. For per-protocol analyses
1894 (see sections 6.2.5 and 6.2.6), data will be presented and analysed by the allocation of the first advanced
1895 airway management used; if neither i-gel nor intubation was used (or if another SGA was used before an i-gel
1896 or intubation), the patients will be excluded from per-protocol analyses.

1897 All analyses and data presentation will be by intention to treat unless otherwise stated in the Table heading.

1898 All outcomes listed in Sections 2.3 and 2.4 will be presented as per the template tables **Table T6** to **T8** and
1899 may also be presented graphically. General methods of presentation and assessing intervention effects are
1900 outlined below. For formal comparisons the intubation group will be the reference group. Details specific to
1901 each outcome are described as appropriate. Secondary outcomes 10 to 13 will not be reported in the primary
1902 outcome paper.

Date type	Outcomes
Binary	mRS (at discharge/30days) Initial ventilation success Regurgitation/aspiration Loss of previously established airway Return of spontaneous circulation (ROSC) 72h survival
Categorical	Actual sequence of airway interventions delivered ¹ Airway management in place when ROSC was achieved or resuscitation was discontinued or intervention from A2 paramedic stopped ¹
Continuous	Chest compression fraction

	Duration of ICU stay (presented separately for survivors and patients who die during ICU stay) ¹
	Duration of hospital stay (presented separately for survivors and patients who die during hospital stay) ¹
Time to event	Time from OHCA to when discharge/30 day mRS was assessed ^{1,3} Time to death ² Time to death (up to 72h)
Longitudinal	mRS (at discharge/30days, 3 months and 6 months) EQ-5D index score and visual analogue scale score (at discharge, 3 months and 6 months)

1903 *Note:-*

1904 ¹ These outcomes will be described but not formally compared

1905 ² Time to death will be formally compared in place of length of ICU and hospital stay

1906 ³ This is not a specified outcome but the DMSC raised it as a point of interest.

1907

1908 • **Binary outcomes** will be presented as numbers and percentages of patients in the category of interest.
1909 Outcomes will be compared between intervention groups using logistic regression. The intervention
1910 comparison estimate will be presented as an adjusted odds ratio (OR) with a 95% confidence interval
1911 (95% CI) and p-value. Formal statistical comparisons of treatment effects will only be performed if more
1912 than ten patients in total experience the outcome (with at least one event in each treatment group). .

1913 • **Categorical outcomes** will be presented as numbers and percentages of patients in each category.
1914 Outcomes will be compared between intervention groups using multinomial logistic regression.
1915 Treatment comparison estimates will be presented as adjusted odds ratios (OR) and 95% confidence
1916 intervals (95% CI). .

1917 • **Continuous outcomes** will be summarised by means and SDs in each treatment group, if distributions
1918 are approximately normal. If distributions are non-normal data will be summarised by the median and
1919 IQR or geometric mean (GM) if a logarithmic transformation provides an approximately normal
1920 distribution. Outcomes will be compared using linear regression. For untransformed data treatment
1921 comparisons will be presented as adjusted differences in means with 95% CI, and for logarithmically
1922 transformed data as adjusted ratios of GMs with 95% CI. Due to the large numbers of trial patients not
1923 expected to survive to 30 days/hospital discharge, a two-part zero-inflated modelling approach will also
1924 be considered for EQ5D visual analogue scale and summary index scores. This will comprise a) an
1925 occurrence model, a logistic regression model for the occurrence of death vs survival; b) intensity model,
1926 a log-linear model for the score, conditional on survival. If it is not possible to fit the model, then an
1927 analysis restricted to those who survive to hospital discharge will be considered.

1928 • **Time to event outcome** time to death will be summarised by the median and IQR in each intervention
1929 group. This will be compared using Cox's proportional hazards or parametric models as appropriate. The
1930 choice of model to use will depend on the distribution of the data. The intervention comparison will be
1931 presented as a hazard ratio (HR) and 95% CI if a proportional hazards model is used or time ratios (TR)
1932 and 95% CI if an accelerated failure time (AFT) model is used. Times will be censored at last contact for
1933 patients known to be alive at that time.

1934 • **Longitudinal outcomes** will be summarised for each time point. Binary and continuous outcomes will
1935 be compared using logistic and linear mixed effects methodologies respectively, with the treatment group
1936 and study design variables (see section 6.2.1) fitted as fixed effects, and patient terms as random effects.
1937 If a time x treatment interaction is not statistically significant at the 10% level an overall treatment effect
1938 will be reported. If the interaction is statistically significant the changes in treatment effect with time will
1939 be described. Different variance/covariance structures will be explored, and the structure that provides
1940 the best fit in terms of information criteria such as AIC, BIC and likelihood ratio tests will be used.

1941 **6.2.3 Statistical significance**

- 1942 For hypothesis tests two-tailed p-values < 0.05 are considered statistically significant.
- 1943 **6.2.4 Model assumptions**
- 1944 For all methods outlined underlying assumptions will be checked using standard methods, e.g. residual plots,
1945 tests for proportional hazards, etc. If assumptions are not valid then alternative methods of analysis will be
1946 sought. If outlying observations are found which mean models do not fit the data adequately, such
1947 observations will be excluded from the main analyses and comments made in footnotes.
- 1948 **6.2.5 Subgroup analyses**
- 1949 Two subgroup analyses for the primary outcome are specified in the protocol: Utstein comparator group vs
1950 non-comparator group and arrest witnessed by ambulance staff or not (**Figure F7**).
- 1951
- 1952 Due to concerns regarding ventilation success raised during the trial, a subgroup analysis of the primary
1953 outcome comparing patients whose i-gel or intubation airway management attempt(s) were or were not
1954 ‘successful’ during the first and/or second attempt (see section 5.2 for definition) will also be performed. This
1955 analysis will be performed per-protocol and as such will only include patients who received at least one
1956 advanced airway management attempt using an i-gel and/or intubation tube.
- 1957
- 1958 Subgroup effects will be fitted by adding a “sub-group x intervention” interaction term to the analysis model.
- 1959 **6.2.6 Sensitivity analyses**
- 1960 For the primary outcome, the following sensitivity analyses will be performed:
- 1961
 - ITT analysis including only patients who received at least one advanced airway management attempt
1962 using an i-gel and/or intubation tube.
 - Per-protocol analysis including only patients who received at least one advanced airway management
1963 attempt using an i-gel and/or intubation tube (see section 6.2.5 for additional sub-group analysis for
1964 this outcome).
 - ITT analysis including all patients who were attended by an AIRWAYS-2 paramedic but not
1965 resuscitated.
- 1966
- 1967
- 1968 **6.2.7 Missing data**
- 1969 In all tables missing data will be indicated by footnotes. If the amount of missing data differs substantially
1970 between treatment groups potential reasons will be explored.
- 1971 Missing predictors:
- 1972 There will be no missing data for any of the randomisation factors (by design).
- 1973 Missing outcomes:
- 1974
 - If the proportion of missing data is less than 5% then complete case analysis will be performed (i.e.
1975 excluding cases with missing data).
 - If the proportion of missing data is above 5% multiple imputation methods will be considered. A general
1976 imputation model that uses an iterative procedure to generate imputed values will be used to generate
1977 multiple complete data sets (e.g. using Stata’s mi impute). The model of interest will be the fitted to each
1978 of the complete data sets and effect estimates combined using Rubin’s rules.
- 1979
- 1980 If appropriate (the level of missingness is >20%) then any variables that are predictive of missingness will be
1981 identified, and if there is reason to suggest that an assumption of missing at random (MAR) given these
1982 variables is reasonable then such variables will be adjusted for in the models of interest. These models can be
1983 shown to provide unbiased estimates of the treatment effect and moreover multiple imputation approaches
1984 would not be expected to recover any additional information.
- 1985 **6.2.8 Multiple testing**
- 1986 No formal adjustment will be made for multiple testing. However as previously described formal statistical
1987 comparisons will not be made for outcomes with low event rates and only pre-specified subgroup analyses

1988 will be performed. Consideration will be taken in interpretation of results to reflect the number of statistical
1989 tests performed and the consistency, magnitude and direction of treatment estimates for different outcomes.

1990 **6.3 Safety data**

1991 Safety data are only collected for events which are unexpected and potentially related to the intervention. All
1992 such events will be detailed along with descriptions of patients' airway management pathway. **Table T9**
1993 summarises such events, as captured via serious adverse event (SAE) report forms and full details will also be
1994 given as listings (see **Table T10**).

1995 No formal comparisons between groups will be made as numbers of events are expected to be small.

1996

1997 **7. AMENDMENTS TO THE SAP**

Previous version	Previous date	New version	New date	Brief summary of changes
V1.0	14/02/2018	V2.0	14/04/2018	
Clarified definition of enrolling paramedic to better reflect the protocol and how it is defined in the analysis code – rephrased as “first A2 paramedic on scene” throughout.
 
Corrected typographical errors and updated figure numbers as a figure added to aid interpretation of the data (new Figure F6).
 
Changed ‘Incident (999 call) to first crew arrival (mins)’ to ‘999 call to first crew arrival (mins)’ throughout at the suggestion of the DMSC and TSC.
 
Corrected inconsistent naming of survival status in data derivations.
 
Added new variable ‘Time of 999 call to first A2 paramedic arrival (mins)’ at the suggestion of the DMSC and TSC (Table T4).
 
Added a sentence to clarify what will be reported in the primary outcome paper.
 
For the analysis of the EQ-5D outcomes the following was added ‘If it is not possible to fit the model, then an analysis restricted to those who survive to hospital discharge will be considered.’ to the allow for the fact that the two part model may not be estimable due to the high proportion of deaths.
 
Labelling of tables was clarified and errors in labelling data types (viz. n/% vs. mean/SD or median /IQR) corrected.
 
Figure F1 was revised to improve readability at the suggestion of the

				
DMSC and TSC. A skeleton footnote was added to the revised figure.
 
Added a breakdown of the numbers by group (rather than Trust) in Figure F2. Added a category to the list of reasons for non-approach.
 
Revised Table T1 to increase readability – information presented in column with no descriptive data available was moved to a footnote. Merged the columns ‘Resuscitation attempted, attended by A2, but not eligible’ ‘trial patients’ at the suggestion of the DMSC and TSC.
 
Removed ‘Enrolling paramedic made only one attempt at allocated intervention before swapping’ from Table T2 as this is not considered a protocol deviation.
 
In Table T5, changed ‘Reasons for not receiving airway management’ to ‘Reasons for not reporting at least one airway management attempt’ for clarity.

1998
1999
2000

2001
2002

[figure not shown]

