500 We will seek consent from survivors (or a consultee according to the requirements of the Mental Capacity Act 2005 if
501 the patient lacks capacity) to collect additional data at hospital discharge and 3 and 6 months after OHCA (depending
502 which consent option the participant chooses-see section 9.7.1). We have chosen a 6-month final follow-up because,
503 whilst there are very few additional deaths between 3 and 6 months, quality of life and functional independence in
504 activities of daily living continue to improve during this time [31].

505

506 *All enrolled patients*

- 507 1. Initial ventilation success, defined as visible chest rise.
- 508 2. Regurgitation/aspiration.
- 509 3. Loss of a previously established airway.
- 510 4. Actual sequence of airway interventions delivered.
- 511 5. Chest compression fraction (one ambulance region only, see below).
- 512 6. Return of spontaneous circulation (ROSC).
- 513 7. Airway management in place when ROSC was achieved or the resuscitation was discontinued.
- 514 8. Economic data regarding expenditure and further healthcare contacts.

515

516 *Patients who survive to admission to hospital (estimated 20% of enrolled patients)*

- 517 9. Length of intensive care stay.
- 518 10. Length of hospital stay.

519

520 *Patients who survive to hospital discharge (estimated 9% of enrolled patients)*

- 521 11. Quality of life (using the EQ-5D) at hospital discharge

522

523 *Patients who survive beyond hospital discharge*

- 524 12. Date of death (if applicable)
- 525 13. Modified Rankin scale at 3 and 6 months following OHCA
- 526 14. Quality of life (using the EQ-5D) at 3 and 6 months following OHCA.

527

528 Good quality, continuous CPR is associated with increased survival and improved neurological outcomes following
529 cardiac arrest [24, 32], and the concept of compression fraction has been developed as a standardised way of
530 measuring and expressing this [33]. The compression fraction is defined as the proportion (or percentage) of
531 resuscitation time without spontaneous circulation during which chest compressions are administered: the higher the
532 compression fraction the better the quality of CPR, and the more likely the patient is to survive [34]. Comparing the
533 compression fraction between the two randomisation arms may help to explain the study findings. Measuring and

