534 reporting compression fraction allows heterogeneity between trials to be more consistently described. A suggested
535 mechanism by which SADs may improve outcome from OHCA is a reduction in interruptions to CPR (with an
536 accompanying increase in compression fraction)

537

538 Compression fraction is not routinely measured during OHCA in England, but is technically possible [35].

539 Measurement of compression fraction requires the use of modified defibrillator-monitors, we do not believe it is
540 practical, or affordable, to measure this in all enrolled patients. Instead, we will implement technology that allows
541 compression fraction to be routinely measured during CPR in a sub-set of enrolled patients (for example in one of the
542 four participating ambulance trusts) and collect these data alongside the other outcome measures. This will enable
543 compression fraction to be compared in a subset of the two trial arms, and will also benefit future studies by
544 introducing and evaluating the technology required to routinely measure compression fraction during OHCA.

545

546 **4.7 Sample size calculation**

547

548 In our feasibility study 9% of recruited patients survived to hospital discharge, and this is the current rate of overall
549 survival to discharge reported by English ambulance trusts (see:

550 <http://www.england.nhs.uk/statistics/statistical-work-areas/ambulance-quality-indicators/ambqi-2012-13/>). A 2%
551 improvement in the proportion of patients achieving a good neurological outcome (mRS score of 0-3) would be
552 clinically significant, and similar to the 2.4% difference in survival to discharge between tracheal intubation and SADs
553 reported in a recently published retrospective analysis [18].

554

555 To identify a difference of 2% (8% vs. 10%, i.e. centred on 9%) requires 4,400 patients per group (at the 5% level for
556 statistical significance and 90% power). However, each OHCA is not an independent observation, as the patients are
557 nested within a limited number of attending paramedics. Using data from our feasibility study of 171 paramedics
558 attending 597 OHCA, we estimated the intraclass correlation (ICC) to be <0.001. However, when estimating the
559 sample size we have assumed a conservative estimate for the ICC of 0.005. We estimate that 1,300 paramedics will
560 participate; this gives an adjusted sample size of 4,535 patients per group (9,070 in total). In our feasibility study the

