1791 analyses on an intention to treat basis (ITT). For patients who do not wish for their previously collected data
1792 to be used, we will exclude all data collected after the point of consent (i.e. ward movements, EQ-5D and
1793 follow-up data) from any analyses.

1794 Data on all withdrawals is captured on a specific case report form (CRF), and will be tabulated by allocation
1795 of the enrolling paramedic (**Table T3**).

1796 **3.7 Analysis populations**

- 1797 • **Population 1a:** The analysis population for the primary outcome (mRS at discharge/30-days) is all
1798 patients who receive resuscitation, are attended by an A2 paramedic and meet the eligibility criteria,
1799 i.e. all trial patients. This is also the analysis population for outcome 5 (chest compression fraction),
1800 but limited to two trusts and starting partway through the trial.

- 1801
- 1802
- 1803
- **Population 1b:** The analysis population for the second component of secondary outcome 6 (ROSC on ED arrival) is all patients who receive resuscitation, are attended by an A2 paramedic, meet the eligibility criteria and were conveyed to ED.
- 1804
- 1805
- 1806
- 1807
- **Population 2:** The analysis population for secondary outcomes 1 to 4, 6 and 7 (airway management details, but only covering ROSC during advanced airway management by A2 paramedic for outcome 6) is all trial patients who received at least one advanced airway management attempt by the enrolling A2 paramedic.
- 1808
- 1809
- **Population 3:** The analysis population for secondary outcome 8 (length of initial ICU stay) is all trial patients who were admitted to ICU.
- 1810
- 1811
- 1812
- **Population 4:** The analysis population for secondary outcome 9 (length of hospital stay) is all trial patients admitted to hospital who did not refuse consent (i.e. patients who either consent to active or passive follow-up or who die prior to approach).
- 1813
- 1814
- 1815
- 1816
- 1817
- **Population 5:** The analysis population for secondary outcomes 10 and 13 (EQ-5D health scores and state scores) and secondary outcomes 11 and 12 (time to death after discharge and mRS during follow-up) is all trial patients who consent to active follow-up, survive to 30 days/hospital discharge and provide relevant data for at least one of the three time points (30 days/hospital discharge, 3 months and/or 6 months).
- 1818
- 1819
- 1820

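### ROSC is analysed only in patients who had an advanced airway attempt or were conveyed to ED; both subsets form after allocation, so selection alone can produce a difference between arms

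*Protocol*

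**What the plan says.** Protocol 4.6.2 places ROSC among the outcomes for every enrolled patient, and SAP 2.4 repeats that grouping. Protocol 6.1 commits to analysis by allocation, whatever happens to the patient afterwards.

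SAP 3.7 narrows this:

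- **Population 2** serves outcomes 1 to 4, 6 and 7. It "is all trial patients who received at least one advanced airway management attempt by the enrolling A2 paramedic". For outcome 6 it covers only ROSC during advanced airway management, which SAP 5.4 derives from the advanced attempts on Form E2.
- **Population 1b** serves ROSC on ED arrival. It holds patients who, among other conditions, "meet the eligibility criteria and were conveyed to ED".
- **Population 1a**, all trial patients, serves the primary outcome and compression fraction (the latter in two trusts).

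SAP 6.2.2 lists ROSC among the binary outcomes to be compared by logistic regression. As far as Table T7 can be read, it carries an odds ratio for ROSC during advanced A2 airway management, and none for ROSC during any A2 airway management or on ED admission.

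The same kind of restriction appears elsewhere. SAP 6.2.6 plans an "ITT analysis including only patients who received at least one advanced airway management attempt" with an i-gel or tube, and a per-protocol analysis in the same subset. SAP 6.2.2 defines per-protocol so that "data will be presented and analysed by the allocation of the first advanced" airway management used. SAP 6.2.5 adds, per-protocol, a subgroup analysis of the primary "outcome comparing patients whose i-gel or intubation airway management attempt(s) were or were not" successful.

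**The concern.** ROSC is defined for every enrolled patient, so nothing forces a restricted denominator. Both restrictions depend on events after allocation, and ambulance clinicians are unblinded (Protocol 5.2.2). SAP 3.5 itself notes that no advanced airway may be needed because ROSC has already occurred, so the outcome helps decide who enters Population 2. Conveyance is likewise plausibly linked to whether circulation has returned.

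If the arms differ in who starts an advanced attempt, or in who is conveyed without ROSC, the subsets are no longer comparable. Grouping by allocation does not repair a selected denominator.

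ROSC is a named secondary outcome, and SAP 6.2.8 makes no multiplicity adjustment. A spurious ROSC difference could be read as the mechanism behind the primary result, or as a reason to doubt it. The treated-only sensitivity analyses could be misread in the same way.

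**Working it through.** **1. The plan's own figure.** Protocol 4.7 states: "To identify a difference of 2% (8% vs. 10%, i.e. centred on 9%) requires 4,400 patients per group (at the 5% level for" "statistical significance and 90% power". The two-proportion formula

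n = [1.96·√(2·0.09·0.91) + 1.2816·√(0.08·0.92 + 0.10·0.90)]² / 0.02²

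gives 4,301, or 4,401 with continuity correction, so 4,400 is reproduced. With 7 patients per paramedic and ICC 0.005, the design effect is 1 + 6 × 0.005 = 1.03, and 4,400 × 1.03 = 4,532 against the stated 4,535. The effective size used below is 4,535 / 1.03 = 4,403 per arm.

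**2. What is assumed.** The documents give no rate of advanced-airway use or conveyance by arm. All such rates below are assumptions, and the device has no effect on any outcome. False-positive rates come from a pooled two-proportion test at two-sided 5%, with 4,403 × (share in the subset) patients per arm. Odds ratios are i-gel against intubation.

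**3. Population 2.** Patients are split into an easy group (10–20% of all, ROSC 70–90%) and a hard group (ROSC 20%). In both arms 90% of hard patients have an advanced attempt. Only the share of easy patients with an attempt differs by arm.

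One case in full: easy share 20%, ROSC 70% in easy patients, attempts in 50% (intubation) against 70% (i-gel) of them.

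- Intubation: share in subset 0.20×0.50 + 0.80×0.90 = 0.82; ROSC (0.10×0.70 + 0.72×0.20)/0.82 = 26.1%.
- i-gel: share in subset 0.20×0.70 + 0.80×0.90 = 0.86; ROSC (0.14×0.70 + 0.72×0.20)/0.86 = 28.1%.
- Odds ratio 1.11, false-positive rate 51%. Over all patients ROSC is 30% in both arms.

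| Easy patients with an attempt (intubation vs i-gel) | Population 2 odds ratio | False-positive rate |
|---|---|---|
| 50% vs 50% | 1.00 | 5% |
| 50% vs 60–70% | 1.03–1.15 | 9–77% |
| 40% vs 70% | 1.10–1.24 | 39–99% |

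In the second row overall advanced-airway use differs between arms by only 1 to 4 percentage points.

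**4. Population 1b.** Suppose 20% of all enrolled patients have ROSC at ED in both arms. The scale is borrowed from the Protocol 4.6.2 estimate of survival to admission. The odds ratio then reduces to (intubation patients conveyed without ROSC) / (i-gel patients conveyed without ROSC).

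| Conveyed without ROSC (intubation vs i-gel) | ROSC among conveyed | Odds ratio | False-positive rate |
|---|---|---|---|
| 10% vs 12% | 66.7% vs 62.5% | 0.83 | 62% |
| 20% vs 25% | 50.0% vs 44.4% | 0.80 | 93% |
| 10% vs 15% | 66.7% vs 57.1% | 0.67 | about 100% |

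Exchanging the arms inverts these odds ratios (for example 12/10 = 1.20), so the direction is not fixed.

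**5. Primary outcome in the treated subset (SAP 6.2.6).** Good recovery is 9% overall in both arms. For example, let 15% be easy patients with 40% good recovery; the rest then have (0.09 − 0.06)/0.85 = 3.5%. With attempts in 50% against 70% of easy patients and in 90% of the rest:

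- Intubation: (0.075×0.40 + 0.765×0.0353)/0.84 = 6.8%.
- i-gel: (0.105×0.40 + 0.765×0.0353)/0.87 = 7.9%.

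Across the cases run (easy share 10–20% with 30–50% good recovery; attempts in 50% against 60–70%), the spurious difference is 0.5 to 1.2 points, against a design difference of 2 points. Odds ratios are 1.08–1.18 and false-positive rates 13–48%.

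**6. After the change.** With all trial patients as denominator, every scenario gives an odds ratio of 1.00 and a 5% rejection rate.

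**The case against.** The strongest reply is that the main inference is untouched. The primary outcome uses Population 1a by the first A2 paramedic's allocation, and 72-hour survival and time to death are derived for Population 1, so unconditioned early-survival comparisons exist. Compression fraction and the Utstein and EMS-witnessed subgroups are not conditioned either, and the third sensitivity analysis widens the population. Outcomes 4 and 7 are described, not tested. Ventilation success and airway loss have no meaning without an attempt. Tables T5 and T7 show advanced-airway receipt and ED admission by arm. All of this stands and lowers the severity, but those tables would reveal an imbalance without correcting it.

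Stronger readings are tempting and are not supported:

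- A reader might infer that quicker i-gel insertion necessarily brings early-ROSC patients into the i-gel set. Entry to Population 2 needs an attempt, not successful placement, and any supraglottic device counts. Solo responders in the intubation arm who use an i-gel first therefore stay in. ROSC present before the A2 paramedic arrives cannot result from the allocation. Only ROSC between arrival and first attempt can differ for this reason, and the documents give no figure for it.
- A reader might choose inputs that give larger effects. With total ROSC 28% in both arms and 12% against 18% before any advanced attempt, 16/88 against 10/82 gives an odds ratio of 1.60 (1.23 at 12% against 15%). With good recovery 9% in both arms, no advanced airway in 15% against 22%, and 22% good recovery among those, the treated-only analysis gives 6.7% against 5.3%. That odds ratio of 1.28 equals the design value (0.10/0.90)/(0.08/0.92). None of these rates comes from the documents. The 1.60 and 1.28 lie above the ranges in the working and show what is possible, not what is expected.
- A reader might conclude that the per-protocol analysis must be replaced by an instrumental-variable estimate. The SAP defines its grouping openly. The fault is the label and the weight it may be given, and a complier-average estimate has assumptions of its own.

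**Conclusion.** The point holds for ROSC. The outcome is listed for all enrolled patients, yet the SAP assigns it only to subsets that form after allocation, and no all-patient ROSC estimate is specified. Under assumed rates with no true effect, the odds ratio is about 1.03 to 1.24 in Population 2 and 0.67 to 0.83 in Population 1b. Both size and direction depend on between-arm differences that the documents do not state; with equal selection there is no bias.

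The two treated-only sensitivity analyses and the ventilation-success subgroup share the weakness, and the per-protocol analysis is in substance as-treated. These are secondary or supportive analyses, so this is a change that should be made, not a threat to the primary result.

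**What to change.** - Make the formal ROSC comparison in Population 1a by the first A2 paramedic's allocation: any ROSC yes/no, and ROSC at ED arrival with patients not conveyed counted as no. Add the estimates to Table T7.
- Keep Populations 1b and 2 for ROSC as supportive description.
- Present ventilation success and airway loss as device-conditional description.
- Label the treated-only 'ITT' analysis, the 'per-protocol' analysis (as-treated) and the ventilation-success subgroup as non-randomised comparisons. A complier-average estimate based on allocation is optional.

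The cost is edits to SAP 3.7, 6.2.2, 6.2.5, 6.2.6 and Table T7, plus taking ROSC from the routine ambulance record where the paramedic CRF is missing. Protocol 5.6.2 already provides for extraction from that record, and Protocol 5.6.1 says ROSC is reported nationally for all resuscitated patients.
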